We plan a prospective randomized controlled study with a null hypothesis that patients randomized to a newly developed decision aid in addition to usual care have no difference in decisional conflict compared to patients treated with usual care and the ASSH brochures.

Secondary Null Hypotheses:

Our second aim is to determine if decision aids influence patient satisfaction, clinical outcomes and regret. To address this second aim, we will test the null hypothesis, which is that there is no difference in the rate of satisfaction, clinical outcomes and regret between patients treated with and without a decision aid.

III. SUBJECT SELECTION

Participants will be recruited among patients presenting to Orthopedic Hand Service of Massachusetts General Hospital with moderate or severe TMC arthrosis or CTS or CTD or DRF and or TF. The study physician will confirm the diagnosis and introduce the study to the patient. Each participant following the explanations by the interventionist will sign a detailed consent form at the time of their baseline diagnostic assessment. The consent form will include all of the study procedures, information about potential risks and benefits of participation, and information regarding who they can contact for further questions. It also will state that participation is voluntary, that participants can refuse to answer any question, and that they can withdraw from the study at any time, and that study participation is in no way related to their care. For follow-up, participants may be contacted by mail, phone and email.

Inclusion criteria:

All adult (>18years old) English-speaking patients presenting to one of the participating hand surgeons, [name], [name], [name] and [name] from the Massachusetts General Hospital with moderate or severe TMC arthrosis, CTS, CTD, DRF and TF will be invited to enroll.

Exclusion criteria include:

1. Patients with prior operative treatment or corticosteroid injection for TMC, CTS, CTD, DRF and TF on the same limb.
2. Patients that have previously used the Decision Aids

IV. SUBJECT ENROLLMENT

The study will be described in detail and the treating physician/study staff will obtain informed consent. Patients will be given a copy of the consent form and be informed that their participation is voluntary and that they may refuse at anytime. The enrolling physician will emphasize that participation is voluntary.

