All patients will be randomized to either a cohort managed with a decision aid (Cohort I) or to a cohort managed without a decision aid (Cohort II). A research fellow does the randomization after the first consult at the outpatient clinic with a computer generated simple randomization sequence.

V. STUDY PROCEDURES

This study will employ a randomized, prospective design. The baseline data are gathered at enrollment. The patients will be randomly assigned to two different cohorts after the encounter with the physician. The physician will be informed that the patient is participating in this study, but will not know to which cohort the patient will be randomized.

Cohort I will be managed with standard care plus a decision aid (henceforth “DA”), and cohort II will be managed without one. The patients in Cohort I will receive the DA, which they can complete in a separate room and take home. The decision aids include information on the disease/condition, treatment options, benefits, risks, scientific uncertainties, and probabilities of potential outcomes tailored to the patient’s health risks factors. Additionally, it includes values clarifications such as describing outcomes in functional terms, asking patients to consider which benefits and risks matter most to them, and guidance in the steps of decision making and

discussing their decision with family/friends. It is interactive and dynamic, helping patients clarify their preferences and come to a decision that feels best to them.

Cohort II will receive the standard care including—at the surgeon’s discretion—the American Society of Surgery of the Hand (ASSH) informational brochure. The patients will have the opportunity to read the brochure in a separate, quiet room or take it home. The ASSH - brochure contains anatomic illustrations of the injury and a discussion of surgical and non-surgical treatments for the diseases, and a general description of expected outcomes. Similar to the patients in cohort II, the patients in cohort I can read and complete the DA in a separate quiet room and take the decision aid home.

After randomization all patients will complete the REDCap questionnaires about the conflict in decision-making, which will take approximately 20 minutes. After completing the study procedures, the physician will return to the room and continue with the visit with the patient. The visit will be timed by a member of the study staff.

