Outcome: Measured variables at enrollment – with REDCap, which will take approximately 20 minutes to fill out:

Demographic Questionnaire:

- Age
- Sex
- Ethnicity
- Race
- Marital status
- Education
- Current work status
- Current or previous occupation
- Hand dominance

Primary outcome:

- Decision conflict scale (DCS) – quantifies the state of uncertainty about a course of action.
- 11-point ordinal satisfaction scale – quantifies the satisfaction with overall treatment.
- 11-point ordinal satisfaction scale – quantifies the satisfaction with decision-making.

Secondary outcome

- Knowledge questionnaire
- Stage of decision making
- Decision Self-efficacy Scale
- Acceptability (Cohort 1 will not receive this questionnaire)
- Pain Self efficacy Questionnaire (PSEQ)
- 9-item Shared Decision Making Questionnaire (SDM-Q-9)

Primary health outcomes variables:

- Quick-DASH
- EQ-5D

At follow-up 1 week-1 month and 6 months after enrollment we will have patients complete the following online REDCap questionnaires, which will take approximately 20 minutes:

The decision-making process variables:

- Quick-DASH
- PROMIS Upper Extremity CAT
- DCS
- 11-point ordinal satisfaction scale – quantifies the satisfaction with overall treatment and decision-making.

- 11-point ordinal satisfaction scale – quantifies the satisfaction with decision-making.
- Decision Regret scale (measures distress or remorse after a health care decision)

VI. BIOSTATISTICAL ANALYSIS

Statistical issues

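### As described, the follow-up satisfaction scale combines treatment and decision-making, so no follow-up item measures treatment satisfaction alone; align it with the enrollment item

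*Combined protocol and SAP*

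**What the plan says.** Section V (Study Procedures) opens its enrollment list with "Outcome: Measured variables at enrollment – with REDCap, which will take approximately 20 minutes to fill out". Under the primary outcome heading of that list are two single-concept scales: "11-point ordinal satisfaction scale – quantifies the satisfaction with overall treatment" and "11-point ordinal satisfaction scale – quantifies the satisfaction with decision-making".

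The follow-up list in the same section applies at 1 week to 1 month and at 6 months, both counted from enrollment. It again has two 11-point scales in the same order. The first now "quantifies the satisfaction with overall treatment and decision-making"; the second is the decision-making scale, unchanged. The other follow-up instruments are Quick-DASH, PROMIS Upper Extremity, the Decisional Conflict Scale and the Decision Regret scale.

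On timing, Section V places the decision-conflict questionnaires after randomization and then says: "After completing the study procedures, the physician will return to the room and continue with the visit with the patient". Section III excludes "Patients with prior operative treatment or corticosteroid injection for TMC, CTS, CTD, DRF and TF on the same limb".

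Satisfaction belongs to a stated hypothesis. Section II, Secondary Null Hypotheses, says: "Our second aim is to determine if decision aids influence patient satisfaction, clinical outcomes and regret".

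**The concern.** An item that asks about two things at once gives a score that cannot be attributed to either. Here the two concepts are ones the protocol itself separates at enrollment, and a decision aid could plausibly move one without the other. The aid acts directly on the decision process; any effect on satisfaction with treatment would be less direct.

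Two things are at stake. First, a between-arm difference on the combined scale could come from treatment, from decision-making or from both. Second, Section VI plans paired t-tests for mean scores of the same group on different occasions. If these were applied to this scale, the enrollment and follow-up scores would answer different questions. The text defines an outcome, so it determines what a satisfaction result can be said to show.

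**Working it through.** **Side-by-side reading of Section V**

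| Concept | Enrollment | Follow-up (both times) |
|---|---|---|
| Treatment alone | listed | not listed |
| Decision-making alone | listed | listed |
| Treatment and decision-making together | not listed | listed |

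None of the other follow-up instruments fills the empty cell: they measure upper-limb function, decisional conflict and decision regret.

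**Timing of the treatment-only item.** It is in the enrollment set. Section V puts the post-randomization questionnaires before the physician returns, and Section III excludes earlier surgery or corticosteroid injection for these conditions on the same limb. The answer therefore apparently precedes the treatment being decided. This is an inference from the visit sequence: other earlier care is not excluded, so some patients could be rating care already received.

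**The plan's own figure.** Section VI gives 126 patients in total for 80% power, effect size 0.5 and alpha 0.05. With a two-sided test and 1:1 allocation (both assumed, as neither is stated):

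- n per arm = 2 × (1.96 + 0.8416)² / 0.5² = 2 × 7.849 / 0.25 = 62.8, rounded up to 63
- total = 2 × 63 = 126

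The figure reproduces, and the wording of the satisfaction scale does not affect it.

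**Illustration of dilution.** Assumptions, none of them in the documents: patients answer the combined item as the equal-weight mean of the two concepts; the two concepts have equal SDs; their correlation is r. If only one concept shifts, by 0.5 SD:

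- shift in the mean of the two = 0.5 / 2 = 0.25
- SD of the mean of the two = √((1 + r)/2)
- apparent effect d = 0.25 / √((1 + r)/2)

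| r | d | Power at 63 per arm |
|---|---|---|
| 0 | 0.25 / 0.707 = 0.35 | 51% |
| 0.5 | 0.25 / 0.866 = 0.29 | 37% |
| 0.9 | 0.25 / 0.975 = 0.26 | 30% |
| 1 (limit) | 0.25 / 1 = 0.25 | not tabulated |

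Power is Φ(d × √(63/2) − 1.96); for r = 0 this is Φ(0.354 × 5.612 − 1.96) = Φ(0.02) = 51%. The same d applies whichever concept shifts. A gain in decision satisfaction alone would still move the combined scale, and a gain in treatment satisfaction alone would be diluted on it.

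**The case against.** The strongest reply is that this is a drafting slip. Follow-up has the same number of satisfaction scales as enrollment, in the same order, and the second is again decision-making alone. A first scale meant to cover both would make the second partly redundant. The protocol also states only what each scale quantifies; it does not reproduce the question shown in REDCap. This stands, and it means the text cannot establish what patients are asked. It does not remove the point, because the protocol is the outcome definition available and should be corrected if it is wrong.

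Three further replies also stand:

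- Both arms receive the same follow-up item, so the randomized comparison at each visit remains valid. What is unclear is what a difference would mean.
- The decision-making-only scale is collected at the same follow-ups. It cannot replace a treatment-only item, but it would show a shift in decision satisfaction and help interpret the combined scale.
- Section VI mentions paired tests in general terms and does not assign them to satisfaction.

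A reader might infer that a gain in decision satisfaction will be reported as a gain in treatment satisfaction. The documents do not support that: no reporting rule is given for this item, and the secondary hypothesis refers to satisfaction without naming treatment satisfaction as a separate endpoint.

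**Conclusion.** The point holds as an inconsistency in an outcome definition, and it is minor. As written, no follow-up item measures satisfaction with treatment alone. The only treatment-only item is at enrollment, and a change score on this scale would mix constructs. The gap is confined to treatment satisfaction; decision-making satisfaction, the between-arm comparisons and the sample size are unaffected.

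It is tempting to go further and say that the trial never measures treatment satisfaction cleanly after treatment. The documents do not establish this, because the patient-facing item is not shown and the combined wording may be unintended. Nor does the 0.25 to 0.35 SD range measure any actual loss. It rests wholly on equal weighting, equal SDs and a correlation from 1 down to 0, and no document gives any of these.

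**What to change.** In the Section V follow-up list, describe the first 11-point scale as satisfaction with overall treatment only, matching enrollment, and keep the decision-making scale as it is. Check the fielded REDCap item against that description.

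- If REDCap already asks about treatment alone, only the protocol line needs correcting.
- If REDCap carries the combined wording and no follow-up data exist, change the item too.
- If follow-up data already exist under the combined wording, date the change and report the two versions separately, without pooling them. This splits the follow-up data for that scale, which is the one real cost.

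Otherwise the cost is one line of protocol text, a check of one item and, where needed, one item edit. Which follow-up time should test satisfaction is a separate choice that this correction does not settle. Follow-up is counted from enrollment, so the earlier assessment may precede treatment for some patients even after the wording is aligned.

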knowledge, risk perception, and participation. Furthermore it helped them clarify their values and preferences, and prepare them for the encounter with their physician and deciding on a course of action.¹⁴ In addition, patients who used decision aids were less anxious and more likely to prefer nonoperative treatment, while outcomes were unaffected.³ Most often a decision aid addresses treatment opportunities and tailors questions to clarify patients' wishes, as recommended by the Ottawa Decision Support Framework.¹⁴

Although the literature is clear about the advantages of decision aids in the process of decision-making, studies are inconclusive about the effect of decision aids on patient satisfaction.¹⁵ Of the 86 RCT's identified by Stacey et al., eleven studies measured satisfaction.³ Of these, four studies reported that people exposed to decision aids had higher satisfaction with their choice compared to usual care, and the remaining seven reported no statistically significant difference.¹⁶

Studies that have directly investigated the effect of decision aids in orthopaedic practice are limited and further study is necessary to determine the best way to implement decision aids in a clinical orthopedic practice.⁵⁷⁻¹² Randomized trials evaluating the impact of decision aids on patient knowledge, decisional conflict, satisfaction, and outcomes may have substantial impact in hand surgery where most treatments are elective and address quality of life.

II. SPECIFIC AIMS (Research Objectives)

Primary Study Question:

The objective is to apply decision aids, which are based on the Ottawa Framework and International Patient Decision Aids Standards (IPDAS) criteria, to two randomly selected patient cohorts (Cohort I and Cohort II) for each diagnosis. The diagnoses will include patients with trapeziometacarpal (TMC) arthrosis, carpal tunnel syndrome (CTS), cubital tunnel syndrome (CTD), distal radius fractures (DRF) and trigger finger (TF). Cohort I is comprised of patients managed with a decision aid, and Cohort II is comprised of patients managed without a decision aid. This distinction is made to evaluate whether the use of a decision aid results in different scores on variables reflective of the decision-making process, behavior, health outcomes, communication, and healthcare system.

Primary Null Hypothesis:

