Based on previous studies, scores of 25 or lower on the DCS (0-100) are associated with low decisional conflict and following-through with decisions.¹⁵ On the other hand, scores of 39 or higher are associated with heightened mental conflict resulting in a delay in the decision making.¹⁵ Our study will measure the rate of patients having a conflict in decision-making. A sample size of 126 total patients was chosen to measure our primary outcome with 80% power, 0.5 effect size and an alpha of 0.05. Chi-square tests will be conducted to determine the differences between two categorical variables. Independent Student's t-tests will be performed to determine the differences between continuous and dichotomous variables. Paired samples T-test will be used to compare the mean scores for the same group on different occasions. Pearson's correlation or Spearman correlation will be used to explore the strength of the relationship between the conflict of decision-making and the use of decision aids. Wherever the minimum expected cell frequency is less than five, the Fisher's exact test will be used instead of the Pearson's Chi-square test. All variables with significant ($p < 0.05$) or near significant ($p < 0.08$) relationships will be evaluated with backwards multivariate/binary logistic regression (depending on the outcome variable) Descriptive statistics will be summarized in terms of means, standard deviations or frequencies, and will be calculated at each time point. Incomplete data will be adequately described and mean imputation will be used when deemed necessary. We will use IBM SPSS ® (19) to perform the data analysis.

VII. RISKS AND DISCOMFORTS (Stratify by common and uncommon)

The greatest discomfort associated with participation is the time required to fill out the decision aid and complete the questionnaires. Completing the DA will require approximately 20

minutes, but this can be done at home. The Questionnaires will require approximately 20 minutes at the time of enrollment.

VIII. POTENTIAL BENEFITS

Individuals managed without a DA will not experience any additional benefits, but will also not have any extra risks. Patients managed with a DA, on the other hand, may experience less decisional conflict and improved knowledge about their disease. The study will benefit society as a whole by providing a better understanding of the factors that influence patient decision-making and surgical outcomes for orthopedic problems.

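### Section VI plans a rate of decisional conflict without a cut-off, a control rate or a labelled effect size, so the stated 80% power cannot be tied to that rate

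*Combined protocol and SAP*

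**What the plan says.** Section VI first cites two published DCS benchmarks: "scores of 25 or lower on the DCS (0-100) are associated with low decisional conflict" and "scores of 39 or higher are associated with heightened mental conflict". The next sentence states what will be measured: "Our study will measure the rate of patients having a conflict in decision-making". The sample size follows: "A sample size of 126 total patients was chosen to measure our primary outcome with 80% power, 0.5 effect size", with alpha 0.05. Section VI gives no control rate, target rate, SD, sidedness or name for the effect-size metric.

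Tests are then listed by type of variable. Chi-square, or Fisher's exact test when an expected count is below five, is for categorical variables. For continuous ones, "t-tests will be performed to determine the differences between continuous and dichotomous variables". Section VI adds a Pearson or Spearman correlation between decisional conflict and use of the aid, and a backward regression for variables with p below 0.05 or 0.08.

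Elsewhere the wording leans towards a score. The primary study question in Section II asks "whether the use of a decision aid results in different scores on variables reflective of the decision-making process". The primary null hypothesis is neutral: patients given the aid "have no difference in decisional conflict compared to patients treated with usual care" and the brochures. The secondary null hypothesis uses the word rate for quantities that Section V measures on scales: "there is no difference in the rate of satisfaction, clinical outcomes and regret". Section V lists the DCS under primary outcome as a scale, beside two satisfaction scales, and schedules the DCS at enrolment and again at follow-up.

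**The concern.** A rate needs a rule for who counts as having conflict. Under Section VI a patient scoring 26 to 38 is in neither benchmark group, so the rate could mean above 25, or 39 and over. The two definitions can give quite different event rates and different power.

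Three things are at stake. The 80% power claim cannot be checked for the rate, the only endpoint form that the statistics section states. The cut-off could be chosen once the data are known, as could the choice between a rate and a mean. And fixing the form does not quite fix the test, because the listed correlation addresses the same between-arm comparison.

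Two neighbouring gaps widen the choice. No primary time point is named for the DCS. The two satisfaction scales are listed as primary in Section V, although Section II makes satisfaction a secondary hypothesis.

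**Working it through.** **Inputs from Section VI:** 126 patients, 80% power, effect size 0.5, alpha 0.05. **Assumed, not in the documents:** two-sided test, equal arms of 63, no dropout, equal SDs, and the control rates and score distributions below.

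**1. Reproduce 126.** For a standardised mean difference d = 0.5, n per arm = 2(1.96 + 0.8416)²/0.5² = 62.8, so 63 per arm and 126 in total. Cohen's h = 2·arcsin√p₁ − 2·arcsin√p₂ uses the same formula, so h = 0.5 also gives 62.8, 63 and 126. At 63 per arm, d = 0.5 has 79.5% power by the noncentral t (64 per arm gives 80.1%), and h = 0.5 has 80.1% by the arcsine formula. Two other readings do not fit: one-sided d = 0.5 needs 50 per arm, and a chi-square effect size w = 0.5 needs 32 in total. The stated total therefore does not separate a mean from a rate.

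**2. Power of the rate under each reading.** If 0.5 is d and scores are normal, a control rate p becomes Φ(z(p) − 0.5) with the aid. For p = 0.50 that is Φ(−0.5) = 0.309. If 0.5 is h, it becomes sin²(arcsin√p − 0.25); for p = 0.50 that is 0.260. Power is by exact enumeration at 63 per arm, using Section VI's own rule of chi-square, or Fisher when the minimum expected count is below five.

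| Control rate | Aid rate, d = 0.5 | Power | Aid rate, h = 0.5 | Power |
|---|---|---|---|---|
| 20% | 9.0% | 42% | 4.5% | 79% |
| 30% | 15.3% | 51% | 10.5% | 79% |
| 50% | 30.9% | 62% | 26.0% | 81% |
| 60% | 40.3% | 63% | 35.3% | 82% |
| 80% | 63.4% | 55% | 57.2% | 80% |

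Under h, power falls at lower control rates: about 74% at 15% and 52% at 10%.

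**3. Check with a bounded score.** I assumed beta-distributed scores on 0–100, control mean 25–35, SD 15–20 and d = 0.5. The t-test keeps about 79%. The rate has 58–73% at the cut of 25 and 24–51% at 39, so 24–73% overall. Between 19% and 34% of control patients fall between the two cuts.

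**4. Mean against rate.** Under d, the t-test (about 79%) exceeds every rate figure above. Under h, the t-test on the mean has 94% or more with normal scores and 87% or more with the bounded scores. The mean is at least as powerful in every case computed.

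**5. False positives with no true effect (simulated).** A single fixed cut gives about 5–6%. Reporting whichever of the two cuts is significant gives about 9–10%. Allowing the t-test as a third option gives about 10–12%. The listed correlation was not counted.

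**The case against.** The best defence is that the mean was intended all along. Section II speaks of scores, Section V lists a scale, and the plan uses rate loosely for satisfaction and regret. On that reading 126 is adequate, at 79.5%. This is plausible, but the sentence between the benchmarks and the sample size says rate, and nothing in Section VI withdraws it. Nor would settling on the mean leave only wording to repair, since the correlation and the time point would still be open.

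The opposite defence is that the rate was intended, with 0.5 as h. That reading meets 80% slightly better than the t-test does. The sentence on 39 and over comes directly before the one on the rate, which leans towards 39. But sentence order does not define an endpoint, and no assumed rates are given.

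A reader might go further and infer that the trial is underpowered for its primary endpoint, or that 126 is wrong. The documents do not support that. The number is arithmetically sound on two readings, and the shortfall appears mainly if 0.5 is d and the rate is analysed. It would also be too strong to say that the rate is safe whenever 0.5 is h, because power falls at control rates below 20% and the plan gives none. Nor do the documents say that a cut will be chosen after the data are seen; they leave room for it.

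It is also fair to say that the power ranges depend on the assumed distribution. They are illustrations; the textual gap does not depend on them.

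**Conclusion.** The point stands as an unresolved definition of the primary endpoint and its effect size, and it should be fixed. What the documents establish is this: a rate with no adopted cut-off, no control rate or SD, an unlabelled 0.5, score wording elsewhere, and a total of 126 that fits both a mean and a rate. The stated 80% therefore cannot be tied to the rate.

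The consequence is conditional. If the mean is primary and 0.5 is d, power is about 79.5% before dropout. If the rate is primary and 0.5 is h, power is close to 80% unless the control rate is low. If the rate is primary and 0.5 is d, power is well short of 80% in every case computed. The false-positive cost of about 9–12%, against about 5–6% for a single fixed cut, arises only if the choice is made after the data are seen.

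**What to change.** In Section VI, name one primary analysis: the between-arm difference in mean DCS total score (0–100), by the independent t-test already listed, at one stated time point. The sponsor should confirm that this falls after patients have used the aid. The enrolment questionnaire may not qualify, because Section VII allows the aid to be completed at home. State a standardised mean difference of 0.5, two-sided alpha 0.05, about 63 per arm (simple randomisation does not guarantee equal arms) and power of about 79.5% before dropout.

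Make the proportions at 25 or lower, between the cuts, and 39 or higher secondary. Label the correlation and the backward regression exploratory. In Section V, move both satisfaction scales to secondary, in line with Section II.

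If the sponsor keeps the rate as primary, fix one cut-off in advance, say what 0.5 measures, state the assumed rate in each arm, and restate the power at 126. If 0.5 then proves to be d, 80% power would need about 200–320 patients under the normal model at control rates of 20–80%. The bounded scores widen this to about 158–212 at the cut of 25 and 256–614 at 39.

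The preferred route costs a few sentences and two moved lines, with no extra patients or data. Its downsides are that the rate, which some readers find easier to interpret, becomes secondary, and that the stated power falls slightly below 80%.

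### Section VI names no primary analysis, and its p<0.08 backward regression neither keeps the randomized arm nor bars variables measured after randomization

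*Combined protocol and SAP*

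**What the plan says.** The primary null hypothesis (Section II) is that decisional conflict does not differ between the arms. Section VI could test this in several ways:

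- A test for categorical data: "Chi-square tests will be conducted to determine the differences between two categorical variables", with Fisher's exact test for sparse tables.
- Student's t-tests, which "will be performed to determine the differences between continuous and dichotomous variables".
- A Pearson or Spearman correlation between conflict in decision-making and use of decision aids. Of the analysis sentences, only this one names both decisional conflict and decision aids.
- A regression: all variables with p<0.05 or near-significant p<0.08 "relationships will be evaluated with backwards multivariate/binary logistic regression (depending on the outcome variable").

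None is tied to the primary hypothesis. For the regression there is no forced term, candidate list or removal threshold. Section VI says the study measures a rate of patients in conflict, while the Section V outcome list gives the Decision Conflict Scale (DCS) as a scale. On size: "A sample size of 126 total patients was chosen to measure our primary outcome", with 80% power, effect size 0.5 and alpha 0.05.

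On timing, Section V states that "After randomization all patients will complete the REDCap questionnaires about the conflict in decision-making", but also that "The baseline data are gathered at enrollment". The same section lists knowledge, decision self-efficacy and SDM-Q-9 with the DCS among the enrollment measures. That list includes an item given to one cohort only: "Acceptability (Cohort 1 will not receive this questionnaire"). Section VIII says that patients given the aid "may experience less decisional conflict and improved knowledge about their disease".

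**The concern.** Randomization supports a causal reading of the arm comparison only while the arm is in the analysis and the adjusters could not have been changed by it. The Section VI rule protects neither condition. The arm is one candidate among all variables, and a variable that the decision aid itself improves may compete with it. Adjusting for such a variable removes the part of the effect that the two share, and backward elimination may then drop the arm.

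A report could therefore show a significant unadjusted difference beside a final model with no arm in it. With no analysis named as primary, nothing in the plan says which result counts, and the choice could be made after the data are seen.

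**Working it through.** **1. The plan's own figure.** Inputs from Section VI: effect size 0.5, alpha 0.05, power 80%. Assumed because not stated: two-sided test, 1:1 allocation, standardized mean difference.

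n per arm = 2 × (1.960 + 0.842)² / 0.5² = 62.8, rounded up to 63, so 126 in total. This matches. The exact t-test power at 63 per arm is 79.5%.

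The same formula with Cohen's h = 0.5 for two proportions also gives 62.8, so 63 per arm. The sample size thus fits an unadjusted comparison of two means or of two rates and does not show which was intended.

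**2. The arm at the p<0.08 screen.** Normal approximation: 0.5 × √(63/2) = 2.806, less the critical value 1.751, gives Φ(1.055) = 0.854; the exact t-test gives 0.850. The arm fails the screen in about 15% of trials. For rates with h = 0.5 and an assumed control rate of 40–50% (exact binomial), it fails in about 14%. A trial that fails at 0.08 cannot have p<0.05 on that same test, so these trials contain no conflict between test and model.

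**3. Why a competitor can displace the arm.** Let the decision aid shift the competitor by s SD, and let the competitor correlate r with the outcome within arm. Signs are set so that positive r means a better competitor score goes with less conflict. The adjusted arm effect is 0.5 − r × s:

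- (0.2, 0.2): 0.5 − 0.04 = 0.46
- (0.3, 0.3): 0.5 − 0.09 = 0.41
- (0.5, 0.5): 0.5 − 0.25 = 0.25

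**4. How often the conflict occurs.** Simulation with 63 per arm, continuous outcome, total effect 0.5 SD, one competitor, screen at p<0.08 and assumed backward removal at p>0.10:

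| Shift s | Correlation r | t-test p<0.05 but no arm in final model |
|---|---|---|
| 0 | 0.3 | 0.3% |
| 0 | 0.5 | 0.4% |
| 0.3 | 0 | below 0.2% |
| 0.3 | −0.3 | 0.0% |
| 0.2 | 0.2 | 1.3% |
| 0.3 | 0.3 | 5.6% |
| 0.5 | 0.5 | 33% |

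The removal cutoff matters: at (0.3, 0.3) the figure is 14% with p>0.05, 6% with p>0.10 and 3% with p>0.15.

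**5. Which candidates are post-randomization.** The DCS is, by Section V's own statement, and so are all follow-up scales. Hence, when a follow-up outcome is modelled, the enrollment DCS is already a post-randomization candidate. For knowledge, decision self-efficacy and SDM-Q-9 the timing is an inference. They share an enrollment list with the DCS and with a one-cohort item, but the sentence on baseline data leaves room for the other reading.

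**The case against.** The benign reading is that the bivariate tests answer the hypothesis and the regression is a supportive search for factors. Section VIII's aim of understanding what influences patient decision-making fits that. The plan never calls the regression an estimate of the decision-aid effect. This stands, and it confines the problem to the adjusted result; but the plan never says the regression is supportive either.

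Displacement also needs several things at once: a competitor measured after randomization, an aid that has acted by then although Section VII allows it to be completed at home, and a correlation in the displacing direction. Without these the conflict is rare, as the table shows. The simulation covers only a continuous outcome, while Section VI speaks of a rate and of binary logistic regression. These limits stand too.

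Three stronger readings are tempting and not supported:

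- A reader might take the 14–15% screen failures as effects lost to the selection rule. They are ordinary lack of power, in trials where the unadjusted test is not significant either.
- A reader might infer that 126 patients settles the t-test as primary. It fits two rates equally well.
- A reader might infer that the arm will be dropped, or that knowledge is certainly measured after randomization. The plan fails to prevent the first and leaves the second open.

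**Conclusion.** The point holds as a gap in the analysis rule. Section VI offers several routes to the primary hypothesis and names none. Its selection procedure neither keeps the arm nor restricts candidates to pre-randomization variables, and no other section supplies these limits. Confidence in these omissions is high.

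The size is uncertain. It runs from well under 1% of trials, when the competitor is unrelated to arm or not correlated in the displacing direction, through about 1% and 6% at modest values, to about a third at (0.5, 0.5). Shifts, correlations and removal cutoff are all assumed, so confidence in displacement is moderate. It would go too far to infer that the trial's primary comparison is invalid: the unadjusted between-arm test is sound. This should be changed because it is cheap and removes a choice that could otherwise be made after seeing the results.

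**What to change.** In Section VI:

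1. State whether the primary endpoint is the DCS score or the rate in conflict, and name the matching unadjusted between-arm test as primary (t-test for the score, chi-square or Fisher for the rate). The sample size is compatible with either.
2. In any model used to estimate the decision-aid effect, always keep the arm and use only pre-specified covariates measured before randomization.
3. Label the backward selection and the correlation exploratory and not estimates of the decision-aid effect.

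In Section V, state for each enrollment instrument whether it is completed before or after randomization. Those completed after it are then excluded as covariates.

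The cost is one paragraph and a timing column, with no new data and no change to the 126 patients. Whether knowledge explains any effect of the aid could no longer be read off the selected model and would need its own exploratory analysis.
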